### 3. Glossary of terms

AE	Adverse Event
CTRU	Clinical Trials Research Unit
DFU	Diabetic foot ulcer
DIC	Digital image correlation
DPN	Diabetic peripheral neuropathy
eGFR	Estimated glomerular filtration rate
GCP	Good clinical practice
IWGDF	International working group for the diabetic foot
LCH	Leeds Community Healthcare NHS Trust
LOPS	Loss of protective sensation
MTH	Metatarsal head
MRC	Medical Research Council
PI	Principal investigator
PIL	Patient information leaflet
PSS	Plantar shear stress
RGF	Research Governance Framework
RUSAE	Related Unexpected Serious Adverse Event
SAE	Serious Adverse Event
SLIPS	Shear load inductive plantar sensing
STAMP	Strain analysis mapping of the plantar surface
SOPs	Standard Operating Procedures

## 4. Background

Four hundred and sixty-three million adults live with diabetes globally, with prevalence expected to rise to 700 million by 2045.[1] Up to one quarter will develop a diabetic foot ulcer (DFU),[2] with 5-8% of these requiring a major amputation within 1 year.[3] Survival is poor, 5-year mortality following development of a DFU has been estimated at 30.5%, with half of patients undergoing a major amputation dead in 5 years. Ulceration is a multifactorial process with peripheral neuropathy and arterial disease playing central roles. Neuropathy leads to the loss of protective sensation and development of abnormal foot architecture.[4] Loss of protective sensation results in undetected, repetitive trauma to the foot.[4] This effect is compounded by the development of structural abnormalities, which increases plantar stress leading to inflammation and tissue breakdown.[5] Plantar pressure forms the vertical component of the load experienced during normal gait. Plantar shear stress (PSS) forms the tangential component of plantar load. It acts parallel to the foot, usually caused by friction between the foot-surface interface and comprises antero-posterior (AP) and medio-lateral (ML) components. [6] It is suggested that the repetitive, multidirectional nature of PSS, both at surface and subsurface levels is a significant contributor to ulcer formation. [7–12]

The authors have performed a systematic review and meta-analysis to summarise the literature on PSS in the diabetic foot. The results of this meta-analysis demonstrated that patients with diabetes and with a loss of protective sensation sustain greater levels of PSS than healthy controls. It also showed those with a current, or previous ulcer exhibit significantly greater levels of PSS compared with those with loss of protective sensation without a history of ulceration. However, it also identified a wide spectrum of methods of measuring PSS, with no validated gold standard. Most studies were performed 'barefoot'; however, as the cornerstone of management of the diabetic foot is ensuring plantar tissue stress reduction through all weight bearing activities by using appropriate footwear, this form of analysis does not reflect the typical shear stresses that are sustained during a normal day. The review therefore highlighted the need for advances in technology to reliably measure 'in-shoe' shear stress and to transfer this to clinical studies investigating its relationship with ulcer formation.

Sensing platforms and insoles measure PSS and plantar pressure in real-time at the foot-surface interface. The technical challenges involved has led to the development of a new method of measuring the effects of PSS and plantar pressure at the foot-surface interface based upon Digital Image Correlation (DIC). DIC is an optical based technique used to measure displacement and strain. It involves comparing the image of the point or object of interest prior to loading, with those after or during loading. The method utilises DIC software employing algorithms to track blocks of pixels to measure displacement or strain. Strain is defined as the ratio between the deformation of a structure and its original length. In the context of an insole, the strain is determined by the plantar load, the product of both PSS and plantar pressure. Thus, it is hypothesised that the level of strain is a product of the cumulative effect of plantar pressure and shear stress during walking.

### **In-shoe technology**

**‘STrain Analysis Mapping of the Plantar surface (STAMP)’** is an untested method, designed by the University of Leeds to measure ‘in-shoe’ strain patterns on the plantar surface of the foot. The insole comprises a pseudorandom pattern applied to a plastically deformable insole using a temporary tattoo layer. STAMP utilises DIC to track the deformation of the pattern on the surface of the insole following a period of walking. This study will use STAMP to measure peak plantar strain. Peak plantar strain is defined as the maximum strain value within a region.

**‘Shear Load Inductive Plantar Sensing’ (SLIPS)** is a new system designed by the University of Leeds to measure ‘in-shoe’ shear and pressure. SLIPS is a wearable sensing insole which integrates 64 tri-axis soft force sensors, simultaneously measuring both plantar pressure and PSS. This study will use SLIPS to analyse peak PSS, mean peak plantar pressure and pressure time integral (PTI). Peak PSS is the largest shear value within a region per gait cycle. Peak plantar pressure is defined as the largest pressure reading within a region per gait cycle. PTI describes the cumulative effect of pressure over time and is calculated as the sum of the products of plantar pressure per time sample by the duration of that time sample.

**Pedar (Novel gmbh, Munich)**, is a commercially available system used to measure in-shoe plantar pressure. The Pedar system will be used to compare the load measured by the novel systems (STAMP and SLIPS) with pressure data (peak plantar pressure and PTI) from Pedar.

The patient group of interest is those that have developed a plantar DFU as a result of abnormal biomechanical loading. The primary pathological process underlying this is diabetic peripheral neuropathy (DPN) which leads to the development of foot deformities, including hammer toe, claw toe, hallux valgus, prominent metatarsal heads, pes cavus, pes planus and pes equinus (IWGDF definition of diabetic foot deformity).[13] A subset of patients with DFUs may develop these as a result of significant ischaemia due to peripheral arterial disease in the absence of significant biomechanical abnormalities. These patients will not be eligible for inclusion, and will be excluded if they have an opening toe pressure of <40mmHg.

Patients with diabetes are classified as ‘low’, ‘intermediate’ and ‘high risk’ risk of ulceration by NICE (NG 19).[14] Patients at highest risk of ulceration are those with a recently healed ulcer; 40% of patients re-ulcerate within 1-year,[2] and we have therefore selected this group to represent the high-risk group for ulcer formation in this study. Those classified as ‘low risk’, have no risk factors for ulceration other than callus alone. With the lowest risk for ulceration and without DPN or foot deformities; this cohort of patients will be used as the comparison group. This study will investigate plantar strain, PSS and plantar pressure in these two patient groups.

## 5. Aims and objectives

The overall aim is to investigate whether patients with diabetes and a recently healed DFU demonstrate elevated levels of plantar strain, PSS and plantar pressure compared with patients at low risk for ulceration, without a history of DFU.

### Primary objective

The primary objective is to compare peak plantar strain, peak PSS and peak plantar pressure in high-risk patients with diabetes who have a recently healed DFU (DFU group) with patients with diabetes who are at low risk of developing a DFU (Low risk group).

[figure not shown]
### Secondary objectives

- 1) To report the relationship between location of peak plantar strain, peak PSS and peak plantar pressure with location of recently healed ulceration in the DFU group.
- 2) To investigate the relationship between peak plantar strain, peak PSS, peak plantar pressure and PTI at the 1st metatarsal head (MTH), 2nd MTH, 3rd MTH, 4th MTH, 5th MTH, hallux, second toe, toes 3-5, midfoot and heel, and to compare between the DFU and Low risk groups.
- 3) To inform research design for prospective studies investigating peak plantar strain, peak PSS and peak plantar pressure as risk factors for ulceration; including methodology, patient selection and modifications to the technology used.

Technology	Load measured	In-shoe/barefoot	Purpose
STAMP	Peak plantar strain	In-shoe	New technique used for the assessment of plantar strain
SLIPS	Peak PSS, peak plantar pressure and PTI	In-shoe	New insole designed to measure plantar shear and pressure
Pedar	Peak plantar pressure and PTI	In-shoe	Used to investigate the association between the measurements recorded by STAMP and SLIPS and plantar pressure recorded by the gold standard pressure system.

## 6. Flow Diagram

Multidisciplinary Diabetes Limb Salvage Clinics and Community Podiatry

\* Single visit unless technology failure requires a second visit

## **7. Study Design**

The study design is a single centre case-control study. Cases will consist of patients with a recently healed DFU. The Low risk group (control group) will consist of patients with diabetes at low risk of ulceration (NICE NG19 definition).[14] The risk factor of interest is plantar strain, measured using the STAMP technique and PSS measured by the SLIPS insole system.

Upon enrolment, baseline clinical data will be collected for each patient. All patients will undergo assessment using STAMP and Pedar systems. If eligible, this will be followed by assessment with the SLIPS system within the same visit.

### **7.1 Blinding**

To reduce the risk of measurement bias during data collection, the order of tests will be randomised using the Latin square method.

To reduce the risk of observer bias, data will be analysed in batches, with the assessor blinded to patient group.

A subsample of 10% of the patients will undergo analysis by a second assessor, also blinded to patient group and level of agreement analysed.

## **8. Eligibility**

### **8.1 DFU group**

Inclusion criteria

All patients with diabetes who have a recently healed plantar DFU will be identified by the clinicians within the Diabetes Limb Salvage Service and assenting patients will be assessed for eligibility by the research team. Patients will undergo STAMP and Pedar assessment if they fulfil the following inclusion criteria:

- 1)  $\geq 18$  years of age
- 2) A diagnosis of diabetes mellitus
- 3) A diagnosis of diabetic peripheral neuropathy (DPN)
- 4) Recently healed plantar DFU (healed within the last 3 months)
- 5) Provide informed written/witnessed verbal consent to participate

Exclusion criteria

Patients will be ineligible if they meet the any of the following exclusion criteria:

- 1) Those who are unable to mobilise independently 150m, without the use of walking aids and thus unable to complete the walking assessment
- 2) Previous ipsilateral minor amputation
- 3) Previous ipsilateral surgical offloading procedure
- 4) Previous contralateral major amputation
- 5) Ipsilateral toe pressure <40mmHg
- 6) Previous open or endovascular ipsilateral revascularisation

#### SLIPS assessment inclusion criteria

The SLIPS insole has been designed to measure the plantar load of the right foot, and due to its size, can only be accommodated by a size 8-11 shoe. The insole is also only able to accommodate patients weighing <100kg. Therefore, in addition to the above criteria, patients will undergo SLIPS assessment if they fulfil the following additional inclusion criteria:

- 1) Recently healed plantar DFU located on the right foot
- 2) The right foot can be accommodated in a size 8-11 shoe
- 3) Weight <100kg

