#### SLIPS assessment inclusion

Consenting patients will also undergo SLIPS assessment if they fulfil the following additional inclusion criteria:

- 1) The right foot can be accommodated by a size 8-11 shoe.
- 2) Weight < 100kg

Patients will be ineligible if they meet any of the following exclusion criteria:

- 1) Those who are unable to mobilise independently 150m, without the use of walking aids and thus unable to complete the walking assessments
- 2) Toe pressure < 40mmHg
- 3) Presence of a foot deformity
- 4) Previous ipsilateral minor amputation
- 5) Previous contralateral major amputation

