## 14. Outcomes

### Primary outcome:

The primary outcome is the difference in peak plantar strain and peak PSS between the DFU and Low risk groups as measured by:

- 1) STAMP
- 2) SLIPS

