## 15. Statistical considerations

### Sample size

The STAMP method is a novel technique, as such nil data exists in the literature to determine a sample size. SLIPSTREAM is a preliminary study and due to the time and resource constraints of an MD project it is not expected to be powered to detect statistical significance. Based upon preliminary work, it is expected the mean difference will be 4, with a standard deviation of 6. Therefore 28 patients per group are required for 90% significance at a power of 80%.

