## Secondary outcome analyses

- 1) Regional analysis: A masking algorithm will be utilised to map the previously defined areas of interest (Measured at the standard ten regions heel, mid foot, 1st MTH, 2nd MTH, 3rd MTH, 4th MTH, 5th MTH, hallux, second toe and toes 3-5) following data acquisition. Intergroup comparisons will be performed comparing mean peak plantar strain at each region using linear regression. Multiple regression analysis will be used to explore the relationship between correlated continuous variables and the risk group. This method will also be utilised to perform regional intergroup comparisons for peak PSS, peak plantar pressure and PTI.
- 2) Peak PSS between DFU and Low risk groups will be compared using linear regression. Bivariable analysis using Pearson's correlation coefficient will be performed to investigate the relationship between the continuous independent variables and mean peak plantar strain. Multiple regression analysis will be used to explore the relationship between correlated continuous variables and the risk group. This method will also be used to perform comparisons between groups for peak plantar pressure and PTI.
- 3) Multinomial regression analysis will be used to investigate the relationship between peak plantar strain and ulcer location.
- 4) ~~Regional analysis: A masking algorithm will be utilised to map the previously defined areas of interest (Measured at the standard ten regions heel, mid foot, 1st MTH, 2nd MTH, 3rd MTH, 4th MTH, 5th MTH, hallux, second toe and toes 3-5) following data acquisition. Intergroup comparisons will be performed comparing mean PSS at each region using ANCOVA, adjusting for factors matched..... Evidence of associated will be present if  $r > 0.3$ . Multiple regression analysis will be used including continuous variables with  $r > 0.3$ , risk group and the presence of joint deformity.~~

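### Peak PSS is named as a primary outcome but measured only in SLIPS-eligible patients, and the single sample size (28 per group, 80% power) is not tied to it

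*Combined protocol and SAP*

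**What the plan says.** Section 14 states: "The primary outcome is the difference in peak plantar strain and peak PSS between the DFU and Low risk groups as measured by" STAMP and SLIPS. The primary objective in Section 5 also includes peak PSS.

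Under Section 7, everyone has STAMP and Pedar, and SLIPS follows only for those eligible. Section 8.1 adds three SLIPS conditions for the DFU group: "Recently healed plantar DFU located on the right foot", a right foot that fits a size 8-11 shoe, and weight below 100 kg. Section 8.2 applies two of these to the Low risk group: "The right foot can be accommodated by a size 8-11 shoe", and the same weight limit.

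Section 15 gives one sample size. It opens with "The STAMP method is a novel technique, as such nil data exists in the literature to determine a sample size", says of the study that "it is not expected to be powered to detect statistical significance", then assumes that "it is expected the mean difference will be 4, with a standard deviation of 6" and concludes: "Therefore 28 patients per group are required for 90% significance at a power of 80" per cent. It names no outcome or unit for the 4 and the 6, and does not mention SLIPS or PSS.

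Section 16 places the shear comparison under secondary outcome analyses: "Peak PSS between DFU and Low risk groups will be compared using linear regression".

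Section 9 says that the SLIPS proportion in each group will be monitored and that patients will be sampled selectively by shoe size and weight, to keep the SLIPS groups equal in size. It gives no number.

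**The concern.** A reader who takes Sections 14 and 15 together will apply 28 per group and 80% power to both halves of the primary outcome. For PSS, that is right only if all 28 in each group qualify for SLIPS. Nothing in the plan says how many will.

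The second issue is who is measured. Strain and Pedar pressure are compared between groups in all patients. PSS is compared in a subset defined by shoe size and weight and, in the DFU group only, by ulcer side. Section 16 plans no strain or pressure group comparison restricted to the SLIPS-measured patients. If strain separates the groups and shear does not, or the reverse, the planned group comparisons cannot tell a difference between the two loads from a difference between the two sets of patients.

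**Working it through.** **Inputs.** Difference 4, SD 6, 28 per group, 90% significance, 80% power (Section 15). SLIPS limits (Sections 8.1 and 8.2). Four patients identified a week, half consenting, about one year (Section 15, planned recruitment rate). The share *f* of enrolled patients who qualify for SLIPS is not given and is treated below as an unknown.

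**1. The plan's own figure.** Reading 90% significance as two-sided alpha 0.10:

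n = 2 × (1.645 + 0.842)² / (4/6)² = 27.8, so 28 per group.

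This reproduces the plan. One-sided alpha 0.05 gives the same n; two-sided 0.05 would need 36. Power at 28 per group is 80.2% by the normal approximation and 79.3% by the t-test.

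**2. What remains for PSS if 28 per group are enrolled.** Two quantities are shown:

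- Power: two-sample t-test, two-sided alpha 0.10, borrowing the standardised effect 4/6 = 0.667. The borrowing is an assumption, because no PSS effect is given.
- Half-width of the 90% CI in SD units: t(0.95, n1 + n2 − 2) × √(1/n1 + 1/n2). This needs no assumed effect.

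| SLIPS patients (DFU v Low risk) | How it could arise (assumed) | Power | 90% CI half-width |
|---|---|---|---|
| 28 v 28 | all qualify | 79% | 1.674 × 0.267 = 0.45 SD |
| 25 v 25 | f = 0.90 in both groups | 75% | 1.677 × 0.283 = 0.47 SD |
| 21 v 21 | f = 0.75 in both groups | 68% | 1.684 × 0.309 = 0.52 SD |
| 14 v 28 | half of ulcers right-sided, no other loss | 64% | 1.684 × 0.327 = 0.55 SD |
| 14 v 14 | as above, with SLIPS groups kept equal | 53% | 1.706 × 0.378 = 0.64 SD |

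If the shoe and weight limits remove more patients, power falls further: at f = 0.25 in both groups (7 v 7) it is 32%. These rows show the range; none is a forecast.

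**3. Enrolment needed for 28 with SLIPS data.** This is 28/f per group: 28/0.75, so 38; 28/0.50 = 56; 28/0.25 = 112. The DFU supply is at most 4 × 0.5 × 52 = 104 a year before exclusions. So 28 DFU patients with SLIPS data are reachable within a year if f is at least 28/104 = 27%, but only by enrolling more than 28 or by choosing patients for SLIPS eligibility. The plan gives no number for either route.

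**4. Primary or secondary.** Section 14 lists PSS as primary. The primary outcome analysis in Section 16 covers strain only, and PSS is item 2 of the secondary analyses. The two sections disagree, and the answer decides whether PSS needs its own size justification.

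**The case against.** The strongest reply has four parts.

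- **The study disclaims power.** Section 15 calls it preliminary and not expected to be powered, and the paragraph concerns STAMP. This stands to the extent that PSS does not fall short of a size set for it: no size was set. But the same paragraph goes on to say that 28 per group are required for 80% power, and does not limit that statement to strain.
- **Section 9 manages SLIPS numbers.** Selective sampling covers two of the three limits and may raise the SLIPS count. It aims at equal groups, though, which two equally small groups would satisfy. It sets no minimum and does not address ulcer side. Sampling on shoe size and weight would also make the strain sample more selected.
- **The limits are disclosed device constraints.** Section 8.1 explains them, and secondary objective 3 makes patient selection and changes to the technology outputs of the study. This is fair; the criteria themselves are not the criticism.
- **The measures are related to one another.** Secondary objective 2 examines strain, PSS, pressure and PTI together, which for PSS can only be done in SLIPS-measured patients. So it would be wrong to say that nothing relates them. What is missing is a group comparison of all of them in the same patients.

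A reader might also infer that only a handful of patients will give PSS data and that a null result would therefore be worthless. The documents do not support that. They contain no eligibility rates, the loss could be slight or severe, and very low power figures come from assumed rates with no selective sampling.

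**Conclusion.** The concern holds as a gap in specification, not as a demonstrated shortfall of known size. With 28 enrolled per group, the stated size and power apply to PSS only if every patient qualifies for SLIPS. Across the cases in which between half and nine-tenths of a group qualify, power is about 53% to 75% against a nominal 79%, and it is lower if fewer qualify. Those powers rest on an assumed eligible share and on a unitless effect taken from a STAMP paragraph. The CI half-widths rest on the share alone.

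Two conclusions need no assumption: the status of PSS differs between Sections 14 and 16, and the PSS population is narrower than the strain population, with the ulcer-side limit applying to the DFU group only. This should be corrected because it affects what can be concluded from PSS, alone or set beside strain.

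**What to change.** - **Section 15:** state that 28 per group and 80% power apply to STAMP strain only. Give the expected number with SLIPS data in each group, and say that PSS will be reported as an estimate with its confidence interval and no power claim.
- **Sections 14 and 16:** reconcile whether PSS is primary or secondary. Limit PSS conclusions to SLIPS-eligible patients (right foot, size 8-11 shoe, under 100 kg).
- **Section 16:** add a repeat of the strain and Pedar group comparisons in the SLIPS-measured patients, labelled supportive, so that shear, strain and pressure are compared in the same people.

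The cost is protocol wording and one further analysis of data already being collected; no extra patients are needed. The PSS claim becomes less favourable, and the subset comparison will be as imprecise as the PSS comparison it accompanies. It should therefore be read through its intervals and not through significance.

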## 8.2 Low risk group

#### Inclusion criteria

Potential patients will be identified by clinicians in the community podiatry service and assenting patients will be assessed for eligibility by either the attending clinical team or a member of the clinical research team. Patients will undergo STAMP and Pedar assessment if they fulfil the following inclusion criteria:

- 1) ≥18 years of age
- 2) A diagnosis of diabetes mellitus
- 3) Low risk for DFU according to the NG19 guidelines (no risk factors for ulceration except callus alone)
- 4) Provide informed written/witness verbal consent to participate

